**3.5.2. Laboratory Data**

As this is a cross-over study with no washout period after the end of treatment period I and before the start of treatment period II, baseline is calculated as the last pre-dose assessment prior to administering the study drug at Baseline/Visit 1 (Study Day 1 Week 0).

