6.2.3. Visit 3 (Study Day 42 ±4 days, Week 6)

Visit 3 is at the clinical site and the following procedures and assessments should be made:

- Obtain and record ongoing medications and instruct the subject on the use of concomitant medications ([Section 5.8](#));
- Measure and record vital signs: heart rate, temperature, respiratory rate and blood pressure ([Section 7.2.2](#));
- Conduct brief/limited physical exam ([Section 7.2.4](#));

- Conduct contraception check ([Section 4.4.1](#));
- Collect all used study medication containers (drug accountability);
- Collect all used cartridges and/or injection devices (drug accountability);
- Review and collect subject diary and instruct/provide subject with new subject diary for the remainder of treatment period;
- Injection site assessment;
- Inquire for and record adverse events;
- Inquire for and record injection device complaints;
- Drug Dispensation:
 - Dispense Genotropin to subjects in Sequence 1.
- Inform subject/caregiver of date of next visit and that subject should bring all used and unused study medication containers, used and unused cartridges and/or injection devices, and subject diary to that visit;
- Inform subjects that regarding the next visit (Visit 4):
 - Subjects that will be switching from Genotropin[®] to somatrogon should administer their final injection of Genotropin[®] 36 hours (± 24 hours) prior to Visit 4;
 - Subjects that will be switching from somatrogon to Genotropin[®] should administer their final injection of somatrogon 7 days (± 72 hours) prior to Visit 4.

6.2.4. Visit 4 (Study Day 84 + 4 days, Week 12) – Crossover/Treatment Change

Visit 4 is at the clinical site and is where subjects will be switched based on their assigned sequence from Genotropin[®] to somatrogon or from somatrogon to Genotropin[®].

Subjects who discontinue study treatment prior to beginning Period II of the study will be asked to complete the assessments and procedures outlined in Visit 4 (except for drug dispensation, and dosing and assessments during and after subject injection).

The following procedures and assessments should be made before subject self-injection:

- Obtain and record ongoing medications and instruct the subject on the use of concomitant medications ([Section 5.8](#));

- Measure and record vital signs: heart rate, temperature, respiratory rate and blood pressure ([Section 7.2.2](#));
- Conduct brief/limited physical exam ([Section 7.2.4](#));

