### **3.4. Baseline Variables**

No variables require specific definitions for baseline.

As this is a cross-over study with no washout period after the end of treatment period I and before the start of treatment period II, baseline is calculated as the last pre-dose assessment prior to administering the study drug at Baseline/Visit 1 (Study Day 1 Week 0).

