## 5. GENERAL METHODOLOGY AND CONVENTIONS

The reporting conventions for the study will follow Pfizer's standard operating procedures unless otherwise specified.

For data displays, all tables, listings, and figures will have headers and footers as per the Pfizer's standard operating procedures. At a minimum, the header will contain compound name, protocol number, and page number (X of Y), while the footer will indicate source data, date of reporting dataset creation, and date of the output generated with time.

For summary tables and data listings:

- Data will be summarized by treatment sequence or treatment period and overall where appropriate.
- Descriptive statistics for categorical variables will be count and percentage and will be presented in the format 'n (%)'. Unless otherwise specified, the percentage in summary tables will be calculated using the number of subjects in the population (header N) for each treatment as denominator.
- Descriptive statistics for continuous variables will be number of observations, mean, standard deviation, median, minimum, and maximum.
- Minimum and maximum will be reported to the same level of precision as the original data. Mean and median will be reported to 1 more decimal than the original data. Standard deviation will be reported to 2 more decimals than the original data.
- Model based estimates and confidence intervals will be reported to 1 more decimal than the original data. Standard errors will be reported to 2 more decimal places than the original data. P-values will be reported to 4 decimal places.
- No preliminary rounding will be performed; rounding will only occur after analysis.

- All data collected will be presented in the data listings. Unscheduled assessments or early discontinuation measurements will be presented in the data listings.
- Data from subjects excluded from an analysis population will be presented in the data listings but will not be included in the calculation of summary statistics, where applicable.
- Data listings will be sorted in the order of treatment sequence, subject, and time of assessment, as applicable.

All analyses will be performed using SAS® version 9.4 or higher.

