### 6.2.4. Safety Endpoints

The following safety endpoints will be summarized descriptively in each treated group using the Safety population as described in [Section 4](#).

- Frequency, severity, and relationship of adverse events to somatrogon;
- Serious adverse events;
- Discontinuations due to adverse events;
- Frequency and severity of abnormal lab values;
- Detection of anti-rhGH antibodies (and neutralizing antibodies);
- Detection of anti-somatrogon antibodies (and neutralizing antibodies).

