### 6.6.2. Laboratory Data

Descriptive statistics will be reported for observed and change from baseline laboratory measurements at each visit. Lab tests will be presented alphabetically within each of the following categories:

- Liver function tests;
- IGF-I, IGF-I SDS;
- Hemoglobin A1c.

For each of the following laboratory tests, a shift from baseline will be presented by visit:

- Safety labs (hematology with differential, blood chemistry, liver function tests);
- IGF-I, IGF-I SDS;
- Hemoglobin A1c;
- Urinalysis.

Categories will be 'Low', 'Normal', and 'High'.

For IGF-I, IGF-I SDS, box plots will be created by visit and treatment group.

The number and percentage of subjects with increases in any of the following will be summarized at each visit and anytime post-baseline:

- ALT >2xULN, >3xULN, <5xULN;
- AST >2xULN, >3xULN, <5xULN;
- Bilirubin >3xULN and ALT >2xULN;
- Bilirubin >3xULN and AST >2xULN.

Two eDISH (evaluation of Drug Induced Serious Hepatotoxicity) scatter plots will be produced: maximum bilirubin vs. maximum ALT and maximum bilirubin vs. maximum AST.

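### Visit 7 lab shifts are taken only from the pre-study value, so an abnormality persisting from Period I is counted again at the end of Period II and cannot be told from a new one

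*SAP*

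**What the plan says.** SAP 3.4 and 3.5.2 define a single baseline, and 3.5.2 applies it to labs: "baseline is calculated as the last pre-dose assessment prior to administering the study drug at Baseline/Visit 1". Both sections give the reason first: "As this is a cross-over study with no washout period after the end of treatment period I and before the start of treatment period II". No Period II reference is defined.

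SAP 6.6.2 uses that baseline twice. On means: "Descriptive statistics will be reported for observed and change from baseline laboratory measurements at each visit". On categories (Low, Normal, High): "For each of the following laboratory tests, a shift from baseline will be presented by visit". The ALT, AST and bilirubin threshold counts "will be summarized at each visit and anytime post-baseline", a span that covers both drugs.

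On presentation, SAP 6.2.4 says of the safety endpoints, which include how often and how severely lab values are abnormal: "The following safety endpoints will be summarized descriptively in each treated group using the Safety population". SAP 5 sets the general layout: "Data will be summarized by treatment sequence or treatment period and overall where appropriate".

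Protocol 9.4 schedules routine labs at Screening, Visit 4 and Visit 7. In Protocol 6.2.4 the fasting Visit 4 bloods fall under the instruction "The following procedures and assessments should be made before subject self-injection", so they precede the first Period II dose.

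**The concern.** With one post-baseline lab visit per drug, the Visit 7 shift is the only shift information on the Period II drug. Measured from the pre-study value, it reflects 24 weeks and both drugs. A subject who turned High in Period I and stays High enters the Visit 7 table exactly as does a subject who first turned High on the Period II drug.

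The SAP handles adverse events differently. Under 3.5.1 an event must be new, or more severe than before, relative to the given treatment. No matching rule exists for labs, and the SAP does not say why.

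At stake is whether the lab safety endpoint can be read by drug. If persistent abnormalities are counted under both drugs, somatrogon and Genotropin look more alike than they are.

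**Working it through.** The documents give no expected rate of lab abnormalities or shifts, so there is no planned figure to reproduce. The check is a trace through the rules, then an illustration under assumed rates.

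**Trace.** Take a subject Normal at Screening, High at Visit 4 and High at Visit 7.

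- Planned shift table: Normal-to-High at Visit 4 and again at Visit 7, once at the end of each drug.
- The adverse event principle of SAP 3.5.1 applied to the same finding: new on the Period I drug; counted on the Period II drug only if worse.

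**What the table can show.** Suppose k subjects in one sequence shift at Visit 4 and k at Visit 7. These may be the same k subjects (all persistent) or different ones (all resolved, k new). Both give the same two counts, so showing the table by sequence and visit does not separate them. Subject-level listings do.

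**Size.** Inputs from the documents: about 90 subjects randomized 1:1 (Protocol 3 and 4.3), so n = 45 per sequence. Assumed: all Normal at baseline; no dropout; a new abnormality with probability p_S on somatrogon and p_G on Genotropin, the same in each period and independent of what went before; a share q of Period I abnormalities still present at Visit 7.

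Shifts from the pre-study value, added up by drug:

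- Somatrogon = n·p_S + n·[p_G·q + (1 − p_G·q)·p_S]
- Genotropin = n·p_G + n·[p_S·q + (1 − p_S·q)·p_G]

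Dividing each by 2n = 90 and subtracting gives: observed difference = (p_S − p_G)·(1 − q/2).

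With p_S = 10% and p_G = 0%:

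| q | Somatrogon shifts | Genotropin shifts | Difference (points) |
|---|---|---|---|
| 0 | 9.0 | 0.0 | 10.0 |
| 0.25 | 9.0 | 1.1 | 8.8 |
| 0.5 | 9.0 | 2.2 | 7.5 |
| 1 | 9.0 | 4.5 | 5.0 |

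At q = 1, for example, Genotropin = 45·0 + 45·0.10 = 4.5, and (9.0 − 4.5)/90 = 5.0 points. With 20% against 2%, the true 18.0 points become 15.8, 13.5 and 9.0 at q = 0.25, 0.5 and 1.

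If Period II shifts are counted only in subjects Normal at Visit 4, the first case gives somatrogon 9.0/90 and Genotropin 0/85.5 (45 + 45·0.90 = 85.5). The difference is 10.0 points at every q.

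**Direction.** Inclusion criterion 2 requires at least 3 months of stable daily growth hormone before screening, so the pre-study value is itself on daily treatment. New abnormalities are then more likely to arise on somatrogon, and carry-over would mainly run from Period I somatrogon to Period II Genotropin. This is an inference, not something that the documents state.

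**The case against.** The single baseline is a deliberate choice with a stated reason, and the Visit 4 value has its own fault: it is taken on treatment. Protocol 1.5 describes the two products as similar in efficacy and safety, so shared class effects are plausible. Suppose both drugs push the same 10% of children to High. The planned table shows 10% for each drug, which is right. Counting only what is new since Visit 4 would show (10 + 0)/2 = 5% for each, half the true figure. A value still High at Visit 7 may be sustained by the Period II drug. This stands, and it rules out simply replacing the pre-study reference with Visit 4.

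A reader might also infer that the tables as planned will halve a true difference. The documents do not support that. SAP 6.6.2 specifies shifts by visit and SAP 5 a layout by sequence or period; no shift table pooled by drug is written, although 6.2.4 does call for summaries per treated group. Halving also needs every abnormality to last from Day 84 to Day 168. That is 84 days, or 84 × 24 / 22.4 = 90 somatrogon half-lives on the half-life in Protocol 1.2. Lab effects can outlast the drug, but nothing in the documents points to full persistence.

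Finally, lab safety is descriptive, no test or decision depends on it, all data are listed, and abnormal results that meet Protocol 8.2.2 are recorded as adverse events and so come under the treatment-specific rule. SAP 6.6 also defers to sponsor reporting standards that are not among the documents. All this limits the consequence. It does not give the summary tables a way to tell persistent from new.

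**Conclusion.** The point holds as a modest gap in the descriptive lab safety summaries. Visit 7 shifts count persistent Period I abnormalities again, the aggregate tables cannot identify them, and this departs from the SAP's own adverse event rule.

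Under the assumed model the between-drug difference is multiplied by (1 − q/2): no loss without persistence, a quarter at 50%, and at most half. The rates, the persistence and the by-drug reading are assumptions.

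Two stronger conclusions are not supported. One is that a common baseline is wrong for shifts and should be replaced; each reference answers a different question. The other is that each drug is charged equally with the other's effects; entry on daily growth hormone suggests a mainly one-way flow, from somatrogon to Genotropin.

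**What to change.** Keep the pre-study baseline for change from baseline and for the planned shift table. Add to SAP 6.6.2, with a matching definition in 3.5.2:

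- A Period II summary, by drug received, that uses the Visit 4 pre-dose value to classify each Visit 7 abnormality as new or worse, or as already present at Visit 4. Attribute only the new or worse ones to the Period II drug.
- A definition of worse, since Low/Normal/High cannot show a rise within High. For ALT and AST, the >2 and >3 × ULN steps already in 6.6.2 would serve.
- Persistent cases on their own line, not dropped. A footnote should say that the Visit 4 reference is an on-treatment value and cannot tell carry-over from an abnormality sustained by the Period II drug.
- The liver threshold counts over all post-baseline time given by treatment period as well.

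Restrict the new summary to subjects dosed in Period II, because Protocol 6.3.3.1.1 also asks those who stop in Period I for Visit 7 labs.

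The cost is SAP wording, one derived reference value and a small table. No extra sampling is needed.

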**4. ANALYSIS SETS (POPULATIONS FOR ANALYSIS)**

Data for all participants will be assessed to determine if participants meet the criteria for inclusion in each analysis population prior to unblinding and releasing the database and classifications will be documented per standard operating procedures.

Population	Description
Enrolled	All participants who sign the informed consent document.
Full analysis set (FAS)	All participants randomly assigned to study intervention and who take at least 1 dose of study intervention. Participants will be analyzed according to the intervention they actually received.

Population	Description
Per protocol set (PPS)	All participants randomly assigned to study intervention and who completed both treatment periods and their corresponding assessments. Participants will be analyzed according to the intervention they actually received.
Safety	All participants who receive at least 1 dose of study intervention. Participants will be analyzed according to the intervention they actually received. A randomized but not treated participant will be excluded from the safety analyses.

## 5. GENERAL METHODOLOGY AND CONVENTIONS

The reporting conventions for the study will follow Pfizer's standard operating procedures unless otherwise specified.

For data displays, all tables, listings, and figures will have headers and footers as per the Pfizer's standard operating procedures. At a minimum, the header will contain compound name, protocol number, and page number (X of Y), while the footer will indicate source data, date of reporting dataset creation, and date of the output generated with time.

For summary tables and data listings:

- Data will be summarized by treatment sequence or treatment period and overall where appropriate.
- Descriptive statistics for categorical variables will be count and percentage and will be presented in the format 'n (%)'. Unless otherwise specified, the percentage in summary tables will be calculated using the number of subjects in the population (header N) for each treatment as denominator.
- Descriptive statistics for continuous variables will be number of observations, mean, standard deviation, median, minimum, and maximum.
- Minimum and maximum will be reported to the same level of precision as the original data. Mean and median will be reported to 1 more decimal than the original data. Standard deviation will be reported to 2 more decimals than the original data.
- Model based estimates and confidence intervals will be reported to 1 more decimal than the original data. Standard errors will be reported to 2 more decimal places than the original data. P-values will be reported to 4 decimal places.
- No preliminary rounding will be performed; rounding will only occur after analysis.

- All data collected will be presented in the data listings. Unscheduled assessments or early discontinuation measurements will be presented in the data listings.
- Data from subjects excluded from an analysis population will be presented in the data listings but will not be included in the calculation of summary statistics, where applicable.
- Data listings will be sorted in the order of treatment sequence, subject, and time of assessment, as applicable.

All analyses will be performed using SAS® version 9.4 or higher.

### 5.1. Hypotheses and Decision Rules

For the primary endpoint analysis conducted after all subjects complete their 24 weeks of treatment (Visit 7), the hypothesis will be tested that overall mean Life Interference score (based on the 7 questions) is lower for weekly somatrogon compared to daily Genotropin.

CCI [REDACTED] Therefore, results of the primary endpoint hypothesis test, including the two-sided p-value, will be reported, but the p-value does not need to meet a specific threshold.

The sample size for the study was based on internal expert opinion with the following assumptions using a two-sided type-I error of 0.05:

CCI [REDACTED]

[REDACTED]

Under the above assumptions, a total of 75 subjects are needed at 90% power from a two-sided paired t-test for mean difference for the proposed study using Life Interference as the primary endpoint. CCI [REDACTED]

## **5.2. General Methods**

### **5.2.1. Analyses for Binary Endpoints**

Descriptive statistics of binary data will include the number of non-missing observations and frequencies of the observed endpoint as well as the observed proportions. When appropriate, a two-sided 95% CI for the corresponding proportion will be provided using the Wilson score method.

### **5.2.2. Analyses for Continuous Endpoints**

A linear mixed effects model including sequence, period, and treatment as fixed effects and subject within sequence and within-subject error as random effects will be used for analyzing the primary endpoint and continuous secondary endpoints. This model will be used to obtain the estimate, CI, and p-value for the treatment effect and other effects of interest.

### **5.2.3. Analyses for Categorical Endpoints**

Descriptive statistics will include the number of non-missing observations, frequencies and proportions for each category of interest. When appropriate, a two-sided binomial 95% CI for the proportion of a specific category will be provided using the Wilson score method.

### **5.2.4. Analyses for Time-to-Event Endpoints**

Not applicable.

## **5.3. Methods to Manage Missing Data**

Scheduled assessments are the preferred source for visit-level data. If no scheduled assessments are performed for a given visit, and if there are unscheduled assessments performed within the visit window, the last available data within the visit window for a given treatment period will be used for the analysis.

The primary endpoint analysis will be performed on the FAS. In addition, a sensitivity analysis of this endpoint will be performed using the PPS (ie, completers with Week 12 and Week 24 assessments). In general, missing values on outcomes endpoints will not be imputed and will not contribute to the analysis.

For missing safety data, for example, missing dates when required for a calculation in adverse events (AEs), missing severity of an AE, or for start and stop dates of medications used, Pfizer's safety rulebook and the algorithms as implemented within CaPS will be employed.

For somatrogon assay results, values below the limit of quantification (BLQ) at the baseline visit will be treated as 0 in the statistical analysis of the results when required. Internal process for handling missing PK data will be used for concentrations below the limit of quantification, deviations, missing concentrations and anomalous values, and missing pharmacokinetic parameters.

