7.2.1.2. Central Laboratory Tests

A central laboratory will be used to analyze hematology, blood chemistry, liver function, thyroid function, and urinalysis tests (as listed in [Table 1](#) below), as well as hormones and to ensure accuracy and consistency in test results. The central laboratory will transmit all results for protocol tests, scheduled and unscheduled, to the sponsor for inclusion in the clinical data base. Urinalysis will be performed on mid-stream, clean catch specimens.

The following safety laboratory tests will be performed at times defined in the [Schedule of Activities](#) and [STUDY PROCEDURES](#) sections of this protocol.

Table 1. Laboratory Tests

Hematology	Chemistry	Liver Function	Lipid Profile	Urinalysis	Additional
Hemoglobin	BUN	AST	Total Cholesterol	pH	IGF-I
Hematocrit	Creatinine	ALT	HDL Cholesterol	Specific gravity	IGF-I SDS
Red blood cell (RBC) count	BUN/Creatinine Ration	GGT	LDL Cholesterol	Bilirubin	Hemoglobin A1c
Mean cell volume (MCV)	Glucose	Total bilirubin	VLDL	Nitrite	Free thyroxine (FT4)
Mean cell hemoglobin (MCH)	Ca ⁺⁺	Direct bilirubin	Cholesterol	Leukocyte Esterase	Urine pregnancy (WOCBP)
Mean cellular hemoglobin concentration (MCHC)	Na ⁺ , K ⁺ , Cl	Indirect bilirubin	Triglycerides	Glucose (qual)	Serum pregnancy (if needed for WOCBP)
Platelet count	Total CO ₂ (Bicarbonate)	Alkaline phosphatase		Protein (qual)	Somatrogon Level
White blood cell (WBC) count	Uric acid			Blood (qual)	Anti-somatrogon Ab (and neutralizing Ab)
Total neutrophils (Absolute [Abs])	Albumin			Ketones	Anti-rhGH Ab (and neutralizing Ab)
Eosinophils (Abs)	Total protein			Microscopic (if necessary)	
Monocytes (Abs)	LDH				
Basophils (Abs)	Magnesium				
Lymphocytes (Abs)	Phosphorus				
	CK				
	GFR				

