### **3.5. Safety Endpoints**

The following safety endpoints will be analyzed in the study:

- *Frequency, severity, and relationship of adverse events to somatrogon;*
- *Serious adverse events;*
- *Discontinuations due to adverse events;*
- *Frequency and severity of abnormal lab values;*
- *Detection of anti-rhGH antibodies (and neutralizing antibodies);*
- *Detection of anti-somatrogon antibodies (and neutralizing antibodies).*

For the analysis of safety endpoints, the programming standards defined in Pfizer CDISC Safety Rulebook will be followed. Missing dates for study medication, and adverse events (AE's) will be imputed as implemented within the CaPS algorithms with the exception of vital signs which are shown below.

For Vital Signs:

The following out of expected ranges will be used to identify potential values of clinical concern for the vital signs parameters in reporting the summaries and shift tables where appropriate.

Test	Low Range	High Range
Respiratory rate (breaths/min)	10	40
Heart Rate (beats/min)	50	135
Systolic BP (mm Hg)	80	130
Diastolic BP (mm Hg)	40	90
Body temperature (oC)	35	38

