## 9. APPENDICES

### Appendix 1. Data Derivation Details

#### Appendix 1.1. Definition and Use of Visit Windows in Reporting

The visit windows are defined for analysis and reporting purposes only.

Laboratory endpoints will be defined within visit windows determined by the actual day of observation relative to first dose of study drug (Day 1), ie, the actual day = date of assessment – date of first dose of study drug + 1.

The contiguous windows will be used to avoid discarding data. Week will be the time unit with a few exceptions noted in the visit window definitions below.

Visit Label	TARGET VISIT DAY	VISIT WINDOW IN DAYS	
		LOWER	UPPER
Screening	≤0	-99	-31
Baseline / V1 (W0)	1	-30	1
V2 (Week 1)*	8	2	25
V3 (Week 6)	42	26	64
V4 (Week 12)	84	65	90
V5 (Week 13)*	92	91	109
V6 (Week 18)	126	110	148
V7 (Week 24)	168	149	195

Notes:

\*Phone call visits only.

Week 24 is the analysis time point.

In general, window size is ½ the duration of the time between the previous study visit and the next study visit.

Target Visit Day = Current Visit in weeks × 7 + 1.

[Visit Window in Days Lower] = Current Target Visit Day – [(Current Target Visit Day – Previous Target Visit Day – 1) ÷ 2].

[Visit Window in Days Upper] = Current Target Visit Day + [(Next Target Visit Day – Current Target Visit Day – 1) ÷ 2].

CCI [REDACTED]

[REDACTED]

[REDACTED]	[REDACTED]	[REDACTED]	[REDACTED]	[REDACTED]
[REDACTED]	[REDACTED]	[REDACTED]	[REDACTED]	[REDACTED]
[REDACTED]	[REDACTED]	[REDACTED]	[REDACTED]	[REDACTED]
[REDACTED]	[REDACTED]	[REDACTED]	[REDACTED]	[REDACTED]
[REDACTED]	[REDACTED]	[REDACTED]	[REDACTED]	[REDACTED]
[REDACTED]	[REDACTED]	[REDACTED]	[REDACTED]	[REDACTED]
[REDACTED]	[REDACTED]	[REDACTED]	[REDACTED]	[REDACTED]
[REDACTED]	[REDACTED]	[REDACTED]	[REDACTED]	[REDACTED]
[REDACTED]	[REDACTED]	[REDACTED]	[REDACTED]	[REDACTED]
[REDACTED]	[REDACTED]	[REDACTED]	[REDACTED]	[REDACTED]

[REDACTED]

[REDACTED]

CCI [REDACTED]	[REDACTED]	[REDACTED]	[REDACTED]	[REDACTED]
[REDACTED]	[REDACTED]	[REDACTED]	[REDACTED]	[REDACTED]
	[REDACTED]	[REDACTED]	[REDACTED]	[REDACTED]

[REDACTED]

[REDACTED]	[REDACTED]	[REDACTED]	[REDACTED]	[REDACTED]
[REDACTED]	[REDACTED]	[REDACTED]	[REDACTED]	[REDACTED]
	[REDACTED]	[REDACTED]	[REDACTED]	[REDACTED]
	[REDACTED]	[REDACTED]	[REDACTED]	[REDACTED]

[REDACTED]

[REDACTED]

CCI [REDACTED]	[REDACTED]	[REDACTED]	[REDACTED]	[REDACTED]
			[REDACTED]	
	[REDACTED]	[REDACTED]	[REDACTED]	[REDACTED]
[REDACTED]	[REDACTED]	[REDACTED]	[REDACTED]	[REDACTED]

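### For non-liver labs, SAP 6.6.2 specifies only by-visit shift tables fed by one value per window, so an abnormal unscheduled result can be shown as Normal

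*SAP*

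**What the plan says.** - **Selection rule (SAP 5.3).** "Scheduled assessments are the preferred source for visit-level data". If a visit has no scheduled assessment but unscheduled ones fall in its window, then "the last available data within the visit window for a given treatment period will be used for the analysis".
- **Where the windows apply (SAP Appendix 1.1).** "Laboratory endpoints will be defined within visit windows". They run without gaps: V2 is Days 2–25, V3 26–64, V4 65–90, V5 91–109, V6 110–148 and V7 149–195. The reason given is "The contiguous windows will be used to avoid discarding data".
- **When labs are scheduled (Protocol 9.4).** Routine safety labs, IGF-I and HbA1c are drawn at Screening, Visit 4 and Visit 7. Any lab in the V2, V3, V5 or V6 window is therefore unscheduled.
- **Endpoint (SAP 3.5).** "Frequency and severity of abnormal lab values".
- **Tables (SAP 6.6.2).** "For each of the following laboratory tests, a shift from baseline will be presented by visit", in the categories Low, Normal and High. The list covers haematology, chemistry, liver tests, IGF-I, IGF-I SDS, HbA1c and urinalysis. ALT, AST and bilirubin thresholds are also counted at any time after baseline, and the eDISH plots use each child's maximum.
- **Unscheduled values.** "The central laboratory will transmit all results for protocol tests, scheduled and unscheduled, to the sponsor for inclusion in the clinical data base" (Protocol 7.2.1.2). "Unscheduled assessments or early discontinuation measurements will be presented in the data listings" (SAP 5).

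**The concern.** One value per window suits a mean or a box plot at a visit. It suits a count of abnormal results less well. Each treatment has a single scheduled post-baseline draw, so an abnormality that arises and resolves within a 12-week period can be seen only at an unscheduled draw. If a normal value follows in the same window, or the scheduled value in that window is normal, the shift table records Normal.

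The SAP provides any-time capture for the liver thresholds but spells out none for the other tests. IGF-I shows what is at stake. SAP 6.5.3 plans to count children with a dose reduction because IGF-I SDS exceeded 2, yet IGF-I is scheduled only at the end of each period. A reduction made in mid-period on the current treatment would normally rest on an unscheduled value. The report could then count a reduction with no matching High in the IGF-I shift table.

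**Working it through.** The plan states no figure here, so there is nothing to reproduce. I applied the rule to single sequences, then asked how often a detected episode would disappear.

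**1. Rule applied to single sequences**

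| Sequence | Same window? | Table shows | Abnormal value |
|---|---|---|---|
| A. Unscheduled High Day 70, scheduled Normal Day 84 | Yes, V4 | Normal | Lost |
| B. Unscheduled High Day 35, unscheduled Normal Day 45 | Yes, V3 | Normal | Lost |
| C. Scheduled High Day 84, unscheduled Normal Day 88 | Yes, V4 | High | Kept |
| D. Unscheduled High Day 60, scheduled Normal Day 84 | No, V3 then V4 | High at V3 | Kept |

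A loss needs an abnormal unscheduled value and a normal value in the same window that is either scheduled or later.

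**2. Share of detected episodes lost in Period I**

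Assumptions, none of them in the documents: onset is equally likely on each of Days 2–83 (82 days), the abnormality lasts D days, it is first found at an unscheduled draw before Day 84, and it is redrawn every 7 days until normal. The scheduled draw is on Day 84.

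If the first draw is on the day of onset *o* and D is a multiple of 7, the first normal draw is on Day *o* + D. The episode is lost in three cases:
- V2: *o* + D ≤ 25, which gives 24 − D onset days
- V3: *o* + D ≤ 64, which gives 39 − D
- V4: *o* + D ≤ 84, because the scheduled value takes priority, which gives 20 − D

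Negative terms count as zero. An episode that straddles two windows leaves an abnormal last value in the earlier one and is kept.

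- 1 week: 17 + 32 + 13 = 62; 62/82 = 75.6%
- 2 weeks: 10 + 25 + 6 = 41; 41/82 = 50.0%
- 3 weeks: 3 + 18 + 0 = 21; 21/82 = 25.6%
- 4 weeks: 0 + 11 + 0 = 11; 11/82 = 13.4%
- 6 weeks: 0

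If the first draw falls on a random day of the episode, I went through every pair of onset and detection days. This can be done in two ways: require detection before Day 84 for every episode, or drop the episodes not found by then.

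| First draw | 1 wk | 2 wk | 3 wk | 4 wk | 6 wk |
|---|---|---|---|---|---|
| At onset | 76% | 50% | 26% | 13% | 0% |
| Random day, always before Day 84 | 76% | 59% | 43% | 34% | 19% |
| Random day, episodes not found by then dropped | 78% | 64% | 49% | 41% | 26% |

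On the last row's basis, with redraws every 3 or 14 days instead of 7, the range over 1–4 weeks is 36–83%.

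**3. Wider denominator**

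These shares leave out episodes first found at the scheduled Day 84 draw, none of which is lost. Let *u* be the share of episodes that get an unscheduled draw, *s* the second row above, and *q* = (D − 1)/82 the chance that an episode is still abnormal on Day 84. The lost share of all detected episodes is *u·s* / [*u* + (1 − *u*)·*q*].

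- *u* = 10%, 1 week: 0.0756 / (0.10 + 0.90 × 6/82) = 0.0756/0.1659 = 46%
- *u* = 10%, 6 weeks: 0.0194 / (0.10 + 0.90 × 41/82) = 0.0194/0.55 = 4%
- *u* = 5%, 1 week: 0.0378 / (0.05 + 0.95 × 6/82) = 0.0378/0.1195 = 32%
- *u* = 5%, 6 weeks: 0.0097 / (0.05 + 0.95 × 41/82) = 0.0097/0.525 = 2%

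**4. Children affected**

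Assume that 1–10% of the 90 children have an unscheduled abnormal value and that 25–100% of those also have a normal value that displaces it. The number missed lies between 90 × 0.01 × 0.25 = 0.2 and 90 × 0.10 × 1.00 = 9.

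**The case against.** The strongest reply is that the shift table need not be the only count of abnormal labs. SAP 3.5 and 6.6 delegate safety reporting to the sponsor's rulebook and to CaPS, and the rule in SAP 5.3 is worded for visit-level data. CaPS may count every post-baseline value. This stands as a limit on the point: the documents neither show such a count nor rule one out.

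Other parts of the reply also stand:
- The liver threshold counts at any time and the eDISH maxima are not visit-level, so on their wording they keep the value. The closer monitoring in Protocol 8.4.2 concerns transaminases. It does not show that repeats of other tests are mostly recovered values.
- The familiar case of a scheduled abnormal result with a normal repeat stays abnormal.
- Under Protocol 8.2.2, an abnormal result with symptoms, or one that needs further diagnostic tests or intervention, meets the condition on dosing changes, or is judged to be an AE, is recorded as an AE and enters the AE tables. Merely repeating a test does not qualify, so AE reporting narrows the gap without closing it.
- Some extra draws have a harmless cause: Protocol section 6 asks children who did not fast to return for fasting labs.
- Worst-value counts rise with the number of draws. In an open-label trial, closer checking on one product could raise its count.

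A reader might infer that unscheduled values appear only in listings. The SAP says that they will be listed, not that they appear nowhere else, and SAP 5.3 uses them when no scheduled value exists.

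**Conclusion.** The point holds for the by-visit shift tables of haematology, non-liver chemistry, IGF-I, IGF-I SDS, HbA1c and urinalysis. For these tests the SAP spells out no other categorical display of abnormality, and the one-value rule can turn a detected abnormal result into Normal. The gap is one of method as well as wording, because no any-time or worst-value display is specified.

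A reader might go further and conclude that the frequency of abnormal labs is understated overall, or biased towards normal on each product. The documents do not support that: CaPS is not shown, the liver thresholds are covered, and the loss arises only in the same-window pattern above.

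The size is unknown. Given detection at an unscheduled draw before Day 84 and weekly repeats, the loss is about 75–78% for 1-week episodes and 0–26% for 6-week episodes, depending on when they are detected. These shares rest on assumed onset, duration and repeat patterns. With no stated number of unscheduled draws, they do not convert into a number of children. The change is worth making because it is cheap and concerns a stated safety endpoint.

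**What to change.** Keep the rule in SAP 5.3 (scheduled first, otherwise last) for by-visit means, box plots and by-visit shifts. Add to SAP 6.6.2, per treatment and using all scheduled and unscheduled values:

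- a shift from baseline to the worst on-treatment value, with highest and lowest shown separately;
- the number and percentage of children with any abnormal value;
- the number of unscheduled draws, so that a difference in sampling between the products is visible.

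Assign each value to the treatment in use when the blood was drawn. The scheduled Visit 4 sample belongs to Period I, because Protocol 6.2.4 places it before the first Period II injection. If CaPS already counts all post-baseline values, say so in SAP 6.6.2 and cite the output.

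The cost is a few lines of SAP text and one extra derivation on data already held, with no change to trial conduct. The downside is the dependence of worst-value counts on the number of draws, which the third item makes visible but does not remove.
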